
ASSESSMENT SCHEDULE
	
The study will consist of the following visits:
 
 
• Visit 1 (D-28-D-1): Screening
 
• Visit 2 (D1): Baseline, randomization, first study drug administration.
 
• Visit 3 to 11 (Week 2-Week 40): on treatment (during double-blind phase).
 
• Visit 12 (Week 52): End of Treatment (EOT) visit (last SC IMP administration at Week 50 and last oral IMP administration day before Visit 12).
 
• Visit 13 (Week 58): End of Study (EOS) visit.
 
 
At screening and baseline visits, a physical examination to assess disease activity and general health will be performed. Patients will be assessed for active or latent tuberculosis (TB) at baseline and during the study.
 
For an overview of the laboratory tests see the study flow chart below, which includes hematology, chemistry, lipids, glucose, insulin, antinuclear antibodies (ANA), glycosylated hemoglobin A1c (HbA1c), urinalysis, human immunodeficiency virus (HIV), Hepatitis B and C, serum and plasma for biomarkers and a 12-lead electrocardiogram (ECG). A serum pregnancy test for women of child bearing potential (WOCBP) will be obtained at screening as well. Future Use Sample (serum and plasma) used for future analysis (eg, circulating proteins) will be collected from each consenting patient using a separate informed consent form (optional). Blood samples (DNA and RNA for sequencing or gene expression [RNA only]) will be collected from each consenting patient using a separate informed consent form (optional).
 
Safety assessments are done at each study visit and include AEs, serious adverse events (SAEs) and adverse events of special interest (AESIs) including but not limited to neutropenia, thrombocytopenia, elevations in hepatic enzymes leading to

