- b Last administration of sarilumab is at Week 50. Patients will be monitored for at least 30 minutes or up to 2 hours as per country specific requirements after each dose of SC IMP for any signs or symptoms of a hypersensitivity reaction.
- c Patient Reported Outcomes include EQ-5D-3L, FACIT-Fatigue, SF-36v2, HAQ-DI
- d Bone Mineral Density assessment will be performed at the baseline (Visit 2) and Week 52 (Visit 12) using a DXA scan. The scan can be performed within ± 14 days of Visit 2 and within -14 days of Visit 12 and needs to include the lumbosacral and femoral neck regions. However, the baseline visit DXA scan is not required if there is one available within 12 weeks of baseline.
- e Chest X-ray is required during the screening period if no chest imaging (X-ray, CT, MRI) is available within the previous 12 weeks of V1 that clearly documents the exclusion of TB or if it does not follow the local guidelines and requirements for active screening of TB. In countries for which a specific approval procedure for the x-ray is required by a different committee than the local EC/IRB, a chest MRI between V1 and V2 can be performed.
- f Hematology (blood should be drawn before drug administration): Hemoglobin, hematocrit, red blood cell (RBC) count and morphology (if RBC count is abnormal), white blood cell (WBC) differential, platelet count, absolute neutrophil count (ANC).
- g Chemistry (blood should be drawn before drug administration): Sodium, potassium, chloride, bicarbonate, blood urea nitrogen (BUN), creatinine and creatinine clearance, calcium, phosphate, total protein, albumin, alanine aminotransferase (ALT) (SGPT), aspartate aminotransferase (AST) (SGOT), alkaline phosphatase (ALP), total bilirubin, conjugated bilirubin, unconjugated bilirubin, lactate dehydrogenase (LDH), uric acid
- h Anti-nuclear antibody (ANA) will be collected at Visit 2 and EOT visits only.
- i Lipids (blood should be drawn before drug administration): Triglycerides (TG), total cholesterol, high density lipoprotein (HDL) cholesterol, low density lipoprotein (LDL) cholesterol. Fasting is defined as having no food or liquid intake (except water/ice) for six hours or more.
- j Blood should be drawn before drug administration. Fasting is defined as having no food or liquid intake (except water/ice) for six hours or more.

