2.1 ANALYSIS ENDPOINTS

2.1.1 Demographic and baseline characteristics

The baseline value is defined as the last available value prior to the first dose of study medication, SC IMP. For patients randomized but not treated, the baseline value is the last available value up to randomization. For PRO assessments, baseline value is defined as the last available value up to and including the day of administration of the first dose of SC IMP.

All baseline safety and efficacy parameters (apart from those listed below) are presented along with the on-treatment summary statistics in the efficacy and safety sections ([Section 2.4.4](#) and [Section 2.4.5](#)).

Demographic characteristics

The following demographic characteristics will be summarized separately by treatment and overall:

- Sex (Male, Female)
- Race (White, Black or African American, Asian, Native Hawaiian or Other Pacific Islander, American Indian or Alaska Native, Unknown, Not reported)
- Ethnicity (Hispanic or Latino, Not Hispanic or Latino, Unknown, Not reported)
- Region (Region 1 [Western countries], Region 2 [South America], and Region 3 [Rest of the World]); definitions of the regions are provided in [Section 2.5.7](#)
- Age (years)
- Age group (≥ 50 and < 65 , ≥ 65 and < 75 , ≥ 75 and < 85 , ≥ 85 years)
- Weight (kg)
- Weight group (< 60 , ≥ 60 and < 100 , ≥ 100 kg)
- Body mass index (BMI, kg/m^2)
- BMI group (< 25 , ≥ 25 and < 30 , ≥ 30 kg/m^2)
- Smoking status (never, former, current)
- Alcohol habits (never, occasional, monthly, weekly, daily)

Medical or surgical history

Medical or surgical history includes all the relevant findings within the lifetime of the patient.

This information will be coded to a “Lower Level Term (LLT)”, “Preferred Term (PT)”, “High Level Term (HLT)”, “High Level Group Term (HLGT)”, and associated primary “System Organ Class (SOC)” using the version of Medical Dictionary for Regulatory Activities (MedDRA) currently in effect at Sanofi at the time of database lock.

Disease characteristics at baseline

The following baseline disease characteristics as well as the other baseline characteristics will be summarized separately by treatment group:

- PMR signs and symptoms:
 - Morning stiffness (≤ 45 minutes, > 45 minutes)
 - Pain in the shoulders, neck and/or hip girdles

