2.5.4 Windows for time points

Visit windows based on days relative to the first IMP dose will be used to map the efficacy, lab, vital signs, PK and ADA measurements to each scheduled visit (see [Appendix I](#)). The following rule will be applied when mapping the measurements to the visit:

- For the same parameter (i.e., efficacy, lab, or vital signs), if a patient has more than one measurement at different dates within the same visit window, the scheduled measurement that is closest to the target date will be used (in case of tie select the latest). If there is no scheduled measurement within the visit window, the unscheduled measurement that is closest to the target date will be used (in case of tie select the latest).
- When a patient has more than one measurement on the same parameter on the same date, then the one with the later/largest sample ID will be used.
- If there is no measurement for a given parameter in an analysis window, data will be considered missing for the corresponding visit.

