HbA1c	X			X		X			X		X	X	
hs-CRP ^k	X	X	X	X	X	X	X	X	X	X	X	X	
ESR ^k	X	X	X	X	X	X	X	X	X	X	X	X	
Urinalysis ^l	X												
Virology ^m	X												
Serum pregnancy test ⁿ	X												
Urine pregnancy test ⁿ		X		X	X	X	X	X	X	X	X	X	
12-lead ECG	X												
Serum sarilumab ^j		X	X	X		X	X		X ^r			X	X
Antibodies to sarilumab/ADA ^j		X				X			X			X	X
Genotyping and biomarkers^j													

VISIT	V1	V2	V3	V4	V5	V6	V7	V8	V9	V10	V11	V12 (EOT)	V13 (EOS)
DAY	D-28 to D-1	D1	D15 (±3)	D29 (±3)	D57 (±3)	D85 (±3)	D113 (±3)	D141 (±3)	D169 (±3)	D225 (±3)	D281 (±3)	D365 (±3)	D407 (±3)
WEEK		Week 0	Week 2	Week 4	Week 8	Week 12	Week 16	Week 20	Week 24	Week 32	Week 40	Week 52	Week 58
Biomarkers-IL-6 and sIL-6R		X	X			X			X			X	
Immune Cell Phenotyping (Whole Blood) ^o		X		X					X				
Future Use Samples (Serum and Plasma) ^p – Optional		X	X			X			X			X	
DNA ^q - Optional		X											
RNA ^q - Optional		X	X										

AE = Adverse event; D = Day; DNA = Deoxyribonucleic acid; ECG = Electrocardiogram; EOT = End of treatment; EOS = End of study; EQ-5D = EuroQol; ESR = erythrocyte sedimentation rate; EUL = elevate upper limb; FACIT-Fatigue = Functional assessment of chronic illness therapy fatigue scale; GCA = Giant cell arteritis; GTI = Glucocorticoid toxicity index; HbA1c = Hemoglobin A1c; HbsAg = Hepatitis B surface antigen; Hbcore Ab = Hepatitis B core antibodies; HCV = Hepatitis C virus; hs-CRP = High-sensitivity C-reactive protein; IL = Interleukin; IMP = Investigational medicinal product; IRT = Interactive voice response system; MD-VAS = Physician global assessment of disease activity- visual analog scale; Pain VAS = Pain visual analog scale; Pt-VAS = Patient global assessment of disease activity– visual analog scale; RNA = Ribonucleic acid; SAE = Serious adverse event; SF-36v2 = Short form 36v2; V = Visit; Wk = Week.

- a Targeted physical examination: head, eyes, ears, neck and throat, skin, respiratory, cardiovascular, neurologic, lymphatic examinations and abdominal examination.
- b Last administration of sarilumab is at Week 50.
- c Patient Reported Outcomes include EQ-5D-3L, FACIT-Fatigue, SF-36v2, HAQ-DI
- d Bone Mineral Density assessment will be performed at the baseline (Visit 2) and Week 52 (Visit 12) using a DXA scan. The scan can be performed within ± 14 days of Visit 2 and within -14 days of Visit 12 and needs to include the lumbosacral and femoral neck regions.

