Appendix I Visit windows based on day ranges

Visit windows based on days relative to the first IMP dose will be used to map the efficacy, lab, vital signs, PK, and immunogenicity data to each scheduled visit (see [Table 7](#)).

Table 7 - Day range for each scheduled visit in the DB period for efficacy, lab, vital sign, PK and ADA summaries

Visit Label	Target Day	Schedule A ^a	Schedule B ^b	Schedule C ^c	Schedule D ^d	Schedule E ^e	Schedule F ^f	Schedule G ^g	Schedule H ^h	Schedule I ⁱ	Schedule J ^j
Double-Blind Period											
Baseline	1	≤ 1	≤ 1	≤ 1	≤ 1	≤ 1		≤ 1	≤ 1	≤ 1	≤ 1
Week 2	15	>1* - 21							>1* - 21	>1* - 49	
Week 4	29	22-42				>1* - 56	>1* - 56	>1* - 42	22 - 56		>1* - 98
Week 8	57	43-70						43 - 70			
Week 12	85	71-98	>1* - 126	>1* - 126		57 - 126	57 - 126	71 - 98	57 - 98	50 - 126	
Week 16	113	99-126						99 - 126	99 - 140		
Week 20	141	127-154						127 - 154			
Week 24	169	155-196	127 - 224	127 - 266		127 - 224	127 - 224	155 - 196	141 - 266	127 - 266	≥ 99
Week 32	225	197-252						197 - 252			
Week 40	281	253-322	225 - 322			225 - 322	225 - 322	253 - 322			
Week 52	365	≥323	≥ 323	≥ 267	>1*	≥ 323	≥ 323	≥ 323	≥ 267	≥ 267	

a Includes temperature, heart rate, blood pressure, PMR clinical assessments (including disease flare), CRP, ESR

b Includes weight, glucocorticoid toxicity index (excluding bone density assessment)

c Includes physician global assessments (MD-VAS), patient reported outcomes and antibodies to sarilumab/ADA

d Includes bone density assessment, ANA

e Includes hematology: hemoglobin, hematocrit, red blood cell (RBC) count and morphology (if RBC count is abnormal), white blood cell (WBC) differential, platelet count, absolute neutrophil count (ANC) and chemistry: sodium, potassium, calcium, chloride, bicarbonate, total protein, creatinine and clearance, blood urea nitrogen (BUN), uric acid, lactate dehydrogenase (LDH), phosphate, albumin, ALT (SGPT), AST (SGOT), alkaline phosphatase (ALP), total bilirubin, conjugated bilirubin, and unconjugated bilirubin

f Includes HbA1c, fasting glucose, fasting lipids: triglycerides (TG), total cholesterol, HDL, LDL

g Includes urine pregnancy test

h Includes serum sarilumab

i Includes biomarkers-IL-6 and sIL-6R

j Includes immune cell phenotyping (whole blood)

* Includes value measured on day 1 but after the first IMP dose

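### A baseline DXA taken after the first dose but inside the permitted 14 days falls outside the SAP's baseline window, so the Week 52 bone-domain score is undefined for a patient with no pre-dose scan

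*SAP*

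**What the plan says.** **When the scan may be done.** SAP Appendix A, footnote d, states: "The scan can be performed within ± 14 days of Visit 2 and within -14 days of Visit 12". Protocol 1.2, footnote d, has the same sentence, and Protocol 9.2.1.4 and 10.2.2.1 repeat the window. The protocol also waives the scan where a recent one exists: "the baseline visit DXA scan is not required if there is one available within 12 weeks of baseline".

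**What Visit 2 is.** The assessment schedule in the protocol summary describes Visit 2 (D1) as "Baseline, randomization, first study drug administration".

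**What counts as baseline.** SAP 2.1.1: "The baseline value is defined as the last available value prior to the first dose of study medication, SC IMP". The only variants given are for patient-reported outcomes and for randomized patients who were never treated.

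**How scans are assigned to visits.** SAP 2.5.4: "Visit windows based on days relative to the first IMP dose will be used to map the efficacy, lab, vital signs", among other data. Table 7 in Appendix I gives Schedule D ("Includes bone density assessment, ANA") two windows only: Baseline at Day 1 or earlier, and Week 52 for anything after Day 1. The asterisk on the second window means: "Includes value measured on day 1 but after the first IMP dose". If a window holds several values, "the scheduled measurement that is closest to the target date will be used"; if it holds none, SAP 2.5.4 treats the visit as missing.

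**How the result is used.** SAP 2.1.3.2, Table 2, scores the bone domain at -29, 0 or +29 according to whether BMD rose by more than 3%, stayed within 3%, or fell by more than 3%. The score feeds CWS and AIS at Week 52.

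**The concern.** The scan window extends to both sides of the first dose, while the analysis window stops at the first dose. A site that scanned on Day 10 complied with the protocol, yet the SAP does not recognise that scan as a baseline.

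Bone density is the only GTI domain with a single post-baseline assessment, so no intermediate visit can stand in. Without a baseline there is no percentage change and no bone score, even when the patient has two valid scans about a year apart. The programmer would then have to choose between leaving the domain missing and scoring it 0, in endpoints that are reported with an ANCOVA estimate, a 95% CI and a p-value (SAP 2.4.4.2).

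**Working it through.** There is no stated figure to reproduce. The check applies the SAP's rules to each day on which the baseline scan is permitted.

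**Step 1: permitted days.** Visit 2 is Day 1 and the flow chart has no Day 0. Fourteen days before gives Day -14 to Day -1; fourteen days after gives Day 2 to Day 15. Total: 14 + 1 + 14 = 29 days.

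**Step 2: apply Schedule D.**

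| Scan taken | Assigned to |
|---|---|
| Day -14 to Day -1 (14 days) | Baseline |
| Day 1 before the dose | Baseline |
| Day 1 after the dose | Week 52 |
| Day 2 to Day 15 (14 days) | Week 52 |

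So 14 of 29 permitted days (14/29 = 48%), plus the post-dose part of Day 1, fall outside the SAP baseline. This is a share of calendar days, not of patients.

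**Step 3: apply the closest-to-target rule (Week 52 target Day 365).**
- Scans on Day 10 and Day 360: the distances are 355 and 5 days. Week 52 takes Day 360, Day 10 is unused, and baseline is missing.
- A scan on Day 10 only: it is labelled Week 52, and baseline is missing.

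**Step 4: look for a rule that fills the gap.**
- SAP 2.1.3.2 scores missing BMD as no change, but as a consequence of withdrawal before Week 24.
- SAP 2.5.2 scores domains as no change at visits after premature treatment discontinuation.
- SAP 2.5.2 carries forward missing lab measurements. Here there is no earlier value to carry.

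None covers a patient who stays in the study without a baseline scan.

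**Step 5: cost per affected patient if scored 0.** Under SAP 2.1.3.2 a negative domain score counts as 0 in the worsening score.

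| True BMD change | Lost from CWS | Lost from AIS |
|---|---|---|
| Fall of more than 3% | +29 | +29 |
| Within 3% | 0 | 0 |
| Rise of more than 3% | 0 | -29 |

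**Step 6: number of patients (assumption).** If a share f of the 118 had only a post-dose baseline scan:

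| f | 118 × f | Upper bound on shift in an arm's mean, 29 × f |
|---|---|---|
| 2% | about 2 | 0.58 points |
| 5% | about 6 | 1.45 points |
| 10% | about 12 | 2.9 points |
| 25% | about 30 | 7.25 points |

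The upper bound supposes the same share f in the arm and that every affected patient there changed by more than 3% in the same direction. If f is equal in both arms and unrelated to BMD change, scoring these patients 0 shrinks the between-arm difference in this domain by the fraction f.

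**The case against.** **The open Week 52 window is deliberate.** It serves the rule in SAP 2.1.3.2 that EOT bone density counts whenever EOT occurs. That is a good reason not to close the window early in general. It does not require the first two weeks after dosing to belong to Week 52: Protocol 10.4.4 does not require a premature EOT scan within 6 months of the baseline one.

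**Few patients may be exposed.** Anyone with a pre-dose scan, including one from the previous 12 weeks, already meets the Day 1 limit. This stands, and the documents give no count.

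**Scoring 0 is often right.** For a true change within 3%, no change is the correct score. This also stands; only larger changes are misscored.

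Four stronger readings are tempting, and the documents do not support them:

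- *Week 52 values are corrupted.* When a genuine Week 52 or EOT scan exists, the closest-to-target rule selects it. When none exists, a change could not be computed under any window.
- *Affected patients drop out of the ANCOVA.* SAP 2.5.2 imputes components so that the scores can be calculated, and explicitly withholds imputation only from patients with no post-randomization measurements. The covariate does not need a baseline DXA either: Appendix J gives 0 bone points where there is no known history of osteoporosis.
- *The comparison is biased between arms.* Treatment is double-blind, and Appendix A of the protocol gives both arms the same prednisone dose in Weeks 0 and 1. Nothing suggests that scan timing differs by arm; dilution is the likelier effect.
- *The trial's main conclusions are at risk.* The primary endpoint does not use bone density, and SAP 2.4.4.4 names only cumulative corticosteroid dose for testing after it.

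**Conclusion.** The point holds in limited form. Two provisions of the SAP contradict the scan window in the protocol and in the SAP's own flow chart. Followed as written, they leave baseline BMD missing for any patient whose sole baseline scan was taken after the first dose and up to Day 15, with no rule for what comes next.

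The loss is one domain score at Week 52, and it matters only where BMD truly changed by more than 3%. The range of about 2 to 30 patients rests wholly on the assumed 2% to 25%; the sponsor can replace it with a count from the DXA dates and the first-dose dates. The consequence is confined to the GTI secondary endpoints. It is worth correcting because the data already exist and the rule is short.

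**What to change.** For bone density only:

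1. In SAP 2.1.1, add an exception: baseline BMD is the last pre-dose scan and, only if there is none, the earliest scan after the first dose up to Day 15. A permitted scan from the previous 12 weeks already qualifies as pre-dose. Giving pre-dose scans priority matters: a rule based on closeness to Day 1 would choose a Day 3 scan over an available Day -10 scan.
2. In Table 7, separate bone density from ANA. Start the bone-density Week 52/EOT window at Day 16, keep the rule that EOT BMD counts whenever EOT occurs, and leave ANA unchanged.
3. State how the bone domain is scored when baseline BMD is still missing after step 1, and report the number of such patients by arm.

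The cost is a few lines of SAP text and one derivation rule. The downside is small: a scan taken up to 14 days into treatment counts as baseline, as the protocol already allows.

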Appendix J Baseline glucocorticoid toxicity

Approach to calculating the Baseline glucocorticoid toxicity score: Toxicities assigned weighted scores from the Composite Index to establish a baseline glucocorticoid toxicity score

[figure not shown]
Toxicity Domain		Points
Body Mass Index (BMI)	BMI < 27	0
	BMI ≥ 27 but < 30	21
	BMI ≥ 30	36
Glucose Metabolism	HgbA1c < 5.7	0
	HgbA1c < 5.7 but on medication	32
	Hgb A1c ≥ 5.7	32
	HgbA1c ≥ 5.7 and on medication	44
	Diabetic retinopathy, nephropathy, or neuropathy (count only one)	44
Blood pressure	Normotensive: systolic ≤ 120 and diastolic ≤ 85 no medications	0
	Systolic ≤ 120 and diastolic ≤ 85 but on medications	19
	Systolic > 120 and diastolic > 85 no medications	19
	Systolic ≤ 120 and diastolic > 85 no medications	44
	Hypertensive emergency or PRES (count only one)	44
Lipid Metabolism	LDL ≤ target ^a	0
	LDL ≤ target ^a but on medications	10
	LDL > target ^a on no medications	10
	LDL > target ^a on treatment	30
Bone/Tendon	Normal BMD or no known history of osteoporosis	0
	Osteoporosis	29
	Insufficiency fracture secondary to osteoporosis	29
	Osteonecrosis	29
	Tendon rupture while on corticosteroid	29
Glucocorticoid Myopathy	No myopathy	0
	Minor glucocorticoid myopathy	9
	Moderate glucocorticoid myopathy	63
	Severe glucocorticoid myopathy	63
Skin	No skin toxicity	0
	Minor skin toxicity (one or more than one minor skin item)	8
	Moderate skin toxicity (one or more than one moderate skin item)	26
	Severe skin toxicity (one or more than one moderate skin item)	26
Neuropsychiatric	No neuropsychiatric toxicity	0
	Minor (one or more than one minor NP item: insomnia, mania, depression, cognitive)	11
	Moderate (one or more than one moderate NP item: insomnia, mania, depression, cognitive)	74
	Severe (one or more than one severe NP item: insomnia, mania, depression, cognitive)	74
	Psychosis	74
	Glucocorticoid-induced violence	74

Infection	No GTI-relevant infections within the pre-baseline GTI interval of the study	0
	Oral or vaginal candidiasis or non-complicated zoster (<Grade3) within the pre-baseline GTI interval of the study	19
	Grade 3 or Grade 4 infection within the pre-baseline GTI interval of the study	93
Ocular	Increased IOP	33
	Posterior subcapsular cataract	33
	Central serous retinopathy	33
Gastrointestinal	GI perf absence of NSAIDs	33
	PUD without H. pylori	33
Endocrine	Adrenal insufficiency	33

^a Target range of <70 mg/dL will be used for LDL domain.

Signature Page for VV-CLIN-0613825 v1.0

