
3. Blood Pressure (BP) (compared to baseline)
 

a. Improvement in BP:

• Decrease in BP of >10% of baseline without medication increase, unless baseline systolic BP ≤ 120 and diastolic BP ≤ 85 OR

• Decrease in medication without an increase in BP of >10%, unless baseline systolic BP ≤ 120 and diastolic BP ≤ 85

b. No significant change in BP:

• BP within 10% of baseline or systolic BP ≤ 120 and diastolic BP ≤ 85 AND no change in medication OR

• Increase in either systolic or diastolic BP >10% with a decrease in medication OR

• Improvement in systolic or diastolic BP of > 10% with an increase in medication

c. Worsening of hypertension:

 
• Increase in BP of >10% such that the systolic BP exceeds 120 mmHg or the diastolic BP exceeds 85 mmHg without a change in medication OR
 
• An increase in anti-hypertensive medication accompanied by stability or no significant change in both the systolic and diastolic BP
 
 
d. Worsening of hypertension despite treatment:
 
 
• Increase in BP of >10% such that the systolic BP exceeds 120 mmHg or the diastolic BP exceeds 85 mmHg AND an increase in medication
 

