Patients are anticipated to have some GC toxicity at baseline, the AIS would be important in establishing that the new therapy is effective at diminishing any baseline GC toxicity over time. With the AIS, toxicities can be removed if improvement occurs, and added if worsening occurs.

AIS decrease over time means that the treatment is effective in decreasing GC toxicity level, compared to placebo which may show fluctuation of CIS over time. Negative score reflects that toxicities present at baseline (or occurring during the trial) resolved over the treatment period.

The steps to calculate the CWS and AIS at Week 52 are described below.

Step 1: Calculate domain-specific worsening score (for computing CWS in Step 2) and improvement score (for computing AIS in Step 2) at each visit.

For Domains without sub-items (Body Weight, Glucose Metabolism, Blood Pressure, Lipid Metabolism, Bone Health and Steroid Myopathy),

- a) For worsening score, only consider positive domain-specific score at each visit. For domain with a negative domain-specific score, the worsening score will be 0.

- b) For improvement score, all domain-specific scores (could be positive or negative) at each visit will be considered.

The Skin and Neuropsychiatric domains both have sub-items. For the Skin domain, these are Acneiform Rash, Easy Bruising, Hirsutism, Atrophy/Striae, and Erosions/tears/ulcerations. For the Neuropsychiatric domain, these are Insomnia, Depression, Mania, and Cognitive Impairment.

- a) For worsening score, only the item with the highest weight is scored for any GTI interval (typically three months) with the CWS. As an example, if neither insomnia nor depression were present at the baseline visit but there is now mild Insomnia and moderate depression present at follow-up, then only the moderate depression is scored (+63 points).
- b) For improvement score, improvement as well as worsening can be recorded. Because it is conceivable that one item might improve while another worsens, the item of greatest improvement (highest absolute weight) and the item of greatest worsening (highest weight) are recorded for given GTI interval.

For Infection Domain, the worsening score and improvement score handle the scoring of infections differently, because the CWS and AIS reflect reciprocal measures of GC toxicity.

- a) For worsening score, the most severe infection in every GTI interval is scored.

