2.4.4 Analyses of efficacy endpoints

The primary and secondary efficacy endpoints will be analyzed using the ITT population. For patients who reduced dose to sarilumab 150mg during the course of the study, a listing of key efficacy endpoint variables will be provided.

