Descriptive statistics including number, mean, SD, SE, median, minimum, and maximum will be provided by treatment group and by visit for domain-specific GTI score, composite GTI total score, composite worsening score and composite improvement score. For CWS and AIS at Week 52, analysis of covariance (ANCOVA) model with treatment groups and baseline glucocorticoid toxicity score as fixed effects, will be used to test the difference of the least-square means (LS means) between the treatment groups. Difference in LS means and the corresponding 95% CI along with the p-value will be provided.

In addition, descriptive statistics (i.e., counts and percentages) will be provided for not worsening (CWS = 0), worsening (CWS > 0), improved (AIS < 0) and not improved (AIS ≥ 0) at Week 52. Odds ratios and exact 95% CIs of not worsening versus worsening and improved versus not improved will be provided for the comparison between the sarilumab and placebo groups.

Analyses of items in Specific list

Number and percentage of patients with each item in specific list will be summarized by treatment groups and by visit.

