2.4.4.4 Multiplicity issues

If the primary endpoint reaches statistical significance, the secondary endpoint for total cumulative CS dose will be tested next.

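### SAP Appendix J mis-scores baseline blood pressure: untreated isolated diastolic elevation gets 44 points, untreated elevation of both pressures gets 19, and four of eight states have no row

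*SAP*

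**What the plan says.** SAP 2.4.4.2 analyzes CWS and AIS at Week 52 with an "analysis of covariance (ANCOVA) model with treatment groups and baseline glucocorticoid toxicity score as fixed effects". SAP 2.4.4 states: "The primary and secondary efficacy endpoints will be analyzed using the ITT population". The baseline score comes from Appendix J, which says that its points are the Composite Index weights (SAP Table 2).

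The Appendix J blood-pressure block has four rows for pressure and medication, plus an event row (hypertensive emergency or PRES, 44 points). The four rows are:

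- both pressures normal, untreated: 0
- both normal, on medication: 19
- both raised, untreated: 19
- "Systolic ≤ 120 and diastolic > 85 no medications": 44

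In the same table the glucose block reserves its higher weight for "HgbA1c ≥ 5.7 and on medication" (44, against 32 for either condition alone). The lipid block does likewise (30 against 10).

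Two other passages matter for the lesser items. The Step 1 example in SAP 2.1.3.2 takes depression that is absent at baseline and moderate at follow-up, and says "then only the moderate depression is scored (+63 points". On the reference visit, protocol 9.2.1.4 scores change in each domain against baseline, and protocol Appendix C heads BMI, glucose, blood pressure, lipids and bone density the same way. SAP 2.1.3.2 speaks of change per GTI interval and sums the scores from Weeks 12, 24, 40 and 52.

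**The concern.** A patient with only the diastolic pressure raised is scored as more toxic than one with both raised, at the same medication status. In addition, apart from the event row, no patient with raised pressure on medication has a score, and neither does an untreated patient with only the systolic pressure raised. No eligibility criterion sets a blood-pressure limit, so these states can occur.

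The missing-domain rules in SAP 2.5.2 deal with absent laboratory values and absent medication information. They do not cover a state that was observed but has no row. The programmer must then either lose the patient from the ANCOVA or invent a score. Both are unplanned choices in the analysis of named secondary endpoints.

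**Working it through.** **Blood-pressure states.** Systolic (≤120 or >120) × diastolic (≤85 or >85) × medication (no or yes) gives 2 × 2 × 2 = 8 states. The last column applies the Table 2 logic, in which 19 is for pressure *or* medication and 44 is for pressure *and* medication.

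| Systolic | Diastolic | Medication | Appendix J | Table 2 logic |
|---|---|---|---|---|
| ≤120 | ≤85 | no | 0 | 0 |
| ≤120 | ≤85 | yes | 19 | 19 |
| ≤120 | >85 | no | 44 | 19 |
| ≤120 | >85 | yes | no row | 44 |
| >120 | ≤85 | no | no row | 19 |
| >120 | ≤85 | yes | no row | 44 |
| >120 | >85 | no | 19 | 19 |
| >120 | >85 | yes | no row | 44 |

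Four of the eight states are unscored. The inversion between the two printed untreated rows is 44 − 19 = 25 points.

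The complement of systolic ≤120 and diastolic ≤85 is systolic >120 *or* diastolic >85. Protocol Appendix C also uses *or* when it defines worsening: "such that the systolic BP exceeds 120 mmHg or the diastolic BP exceeds 85 mmHg". With *or* in both elevated rows, all eight states are scored once.

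**How many patients.** The documents do not say; the logical range is 0 to 118. If a share p were dropped, the standard error of the LS-mean difference would rise by about 1/√(1 − p). For assumed values of p = 0.1, 0.3 and 0.5 (about 12, 35 and 59 of 118 patients) the factor is 1.05, 1.20 and 1.41. These shares are illustrations, not estimates, and the SAP does not specify deletion.

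**Worked example.** Protocol 9.2.1.4 gives a maximum score of 439. The largest Table 2 weights reproduce it: 36 + 44 + 44 + 30 + 29 + 63 + 26 + 74 + 93 = 439. With 63 as the largest neuropsychiatric weight the sum would be 439 − 11 = 428. Table 2 gives 74 for none to moderate and 63 for mild to moderate, and Appendix J scores moderate as 74. The example's starting state is none, so its score should be +74.

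**Reference visit.** The figures below use the neuropsychiatric weights at Weeks 12, 24, 40 and 52. The patterns are constructed.

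- Absent at baseline, moderate from Week 12 onward. Baseline reference: CWS = 4 × 74 = 296. Prior-visit reference: CWS = 74.
- Moderate at Week 12 only. Baseline reference: AIS = 74. Prior-visit reference: AIS = 74 − 74 = 0.
- Moderate at baseline, none at Week 12, moderate from Week 24. Baseline reference: CWS = 0 and AIS = −74. Prior-visit reference: CWS = 74 and AIS = −74 + 74 = 0. Both the worsening and the improvement category change.

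**The case against.** **A misprint or a conversion fault.** Perhaps a symbol in the fourth row was misread from the PDF. That does not rescue the table. If its systolic sign were >, the third and fourth rows would describe the same state with different points. If the row were meant as both pressures raised on medication, four states (isolated systolic and isolated diastolic, each untreated and treated) would still be unscored.

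**Little depends on it.** This largely stands. One domain of one covariate is affected, in two secondary endpoints outside the stated test sequence: after the primary endpoint, "the secondary endpoint for total cumulative CS dose will be tested next". SAP 2.5.2 also leaves patients without post-randomization measurements with no Week 52 cumulative score, so this ANCOVA was never certain to hold every randomized patient.

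**The proposed rows are inferred.** This stands too. Protocol Appendix C concerns change from baseline, not baseline status. The glucose and lipid analogy is also imperfect, because some of those rows carry no untreated qualifier and, read literally, overlap the medication rows. The source instrument has to settle the wording.

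**The reference visit.** A reader of the SAP alone might infer that no reference visit is stated anywhere. The protocol does state one: baseline. Nor does the SAP's Step 1 example decide the matter, since the first interval starts at baseline under either rule. What remains is a conflict. The SAP's per-interval scoring, its account of CWS as adding new toxicities, and its account of AIS as letting toxicities that arise during the trial resolve all read as a comparison with the previous visit.

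**Conclusion.** The blood-pressure block is wrong as printed: a 25-point inversion, and four of eight states without a score. This rests on the table alone. The number of patients affected is not known.

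A reader might infer that the fault biases the treatment comparison. The documents do not support that. The covariate is measured before treatment in a randomized trial, so the cost is mainly precision, together with an analyst's choice left open. Nor does it reach the primary endpoint, the cumulative corticosteroid dose or the unadjusted analysis in which "Odds ratios and exact 95% CIs of not worsening versus worsening and improved versus not improved will be provided".

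The +63 is an erratum with no effect if Table 2 is programmed. The reference-visit conflict is a separate point held with lower confidence. It could change CWS and AIS values, and in some patterns their categories, but nothing in the documents shows how often such patterns would occur.

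**What to change.** Before unblinding:

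1. Replace the third and fourth blood-pressure rows of Appendix J so that every state is scored once. The reading that fits Table 2 and the glucose and lipid blocks is: systolic >120 *or* diastolic >85, no medications, 19 points; systolic >120 *or* diastolic >85, on medications, 44 points. The sponsor should confirm this against the source instrument.
2. Correct the Step 1 example to +74.
3. State one reference visit for CWS and one for AIS. Reconcile them with protocol 9.2.1.4 and Appendix C, the four-visit sum in Step 3, the per-visit maximum weight in the Table 2 footnote, and the no-change rule after treatment discontinuation in SAP 2.5.2.

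The cost is SAP text and programming. No new data are needed.
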